9.4.3 Method of Assigning Subjects to Treatment Groups

Subjects will be enrolled into 2 cohorts according to mean baseline platelet count ($<40 \times 10^9/L$ or from 40 to $<50 \times 10^9/L$), with neither baseline platelet count cohort comprising greater than 55% of the total number of subjects enrolled into the study. Within each cohort, subjects will be further stratified centrally by risk of bleeding associated with the elective procedure (low, moderate, or high) and HCC status (Yes or No), in order to ensure balance between treatments within each cohort and each further stratum. Within each cohort and each further stratum, subjects will be assigned in a 2:1 ratio to receive avatrombopag or placebo once a day for 5 days

based on a computer-generated randomization scheme using permuted-block randomization. It is planned that no fewer than 10% of subjects will be enrolled into the high risk group and no more than 60% of subjects in the low-risk group. The randomization scheme and identification for each subject will be kept strictly confidential before the database lock and final unblinding, and will be included in the final clinical study report for this study.

Approximately 200 subjects who meet all the eligibility requirements will be randomized. (revised per Amendment 04)

Randomization will be performed centrally by an IxRS. The IxRS or clinical supply vendor will generate the randomized study drug identification numbers. After successful completion of Visit 1, the investigator or designee will call or access via web the IxRS to register the subject information and the IxRS will assign each subject a unique 6-digit randomization number at Visit 2.

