#### 4 DETERMINATION OF SAMPLE SIZE

The proposed sample size was based on comparisons of the primary efficacy variable, with the response rate defined as the proportion of subjects who do not require a platelet transfusion or any rescue procedure for bleeding after randomization and up to 7 days following an elective procedure. Based on clinical opinion and the published results of a similar compound in adults with thrombocytopenia associated with liver disease (ELtrombopag EVALuated for its Ability to overcome Thrombocytopenia and Enable procedures [ELEVATE] study [Afdahl, 2012]), the response rate in the placebo group is assumed to be 18%. Within each baseline platelet count cohort, a sample size of 100 randomized subjects, 67 subjects for avatrombopag and 33 subjects for placebo, would have greater than 90% power to detect an absolute difference of 35% between the avatrombopag response rate and the placebo response rate assuming 18% response rate for placebo using Fisher's Exact tests with a 2-sided  $\alpha=0.05$ . The hypothesized treatment group difference was based on platelet count changes found in the Phase 2 study (E5501-G000-202) and dose-response modeling using data from that study and others in the project development. Based on the baseline data in the Phase 2 study and assuming these were projected to be similar for this study, it was anticipated that this study would enroll roughly half of the total number of subjects in each of the 2 baseline platelet count cohorts to make the total sample size of 200 randomized subjects, 133 subjects for avatrombopag and 67 subjects for placebo.

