### 5.4.1 Primary Efficacy Analyses

The primary efficacy variable is the proportion of subjects who do not require a platelet transfusion or any rescue procedure for bleeding after randomization and up to 7 days following an elective procedure.

The null hypothesis is that the proportion of subjects not requiring a platelet transfusion or any rescue procedure for bleeding after randomization and up to 7 days following an elective procedure is the same between the avatrombopag and placebo treatment groups. The corresponding alternative hypothesis is that the proportion of subjects not requiring a platelet transfusion or any rescue procedure for bleeding after randomization and up to 7 days following an elective procedure is not the same between avatrombopag and placebo. This hypothesis will be tested separately with each baseline platelet count cohort.

The proportion of subjects not requiring a platelet transfusion or any rescue procedure for bleeding will be tested between the individual avatrombopag treatment group (40 or 60mg) and matching placebo within each baseline platelet count cohort ( $<40 \times 10^9/L$  or from 40 to  $<50 \times 10^9/L$ ), each at a significance level of  $\alpha=0.05$  using the generalized Cochran Mantel Haenszel (CMH) test adjusting for the risk of bleeding associated with the elective procedure (low, moderate, or high based on Amendment 02 categorization).

- For subjects with platelet count  $<40 \times 10^9/L$  at baseline, the treatment comparison will be carried out between the 60 mg avatrombopag treatment group (Group A) versus matching placebo (Group B).
- For subjects with platelet count from 40 to  $<50 \times 10^9/L$  at baseline, the treatment comparison will be carried out between the 40 mg avatrombopag treatment group (Group C) versus matching placebo (Group D).

This study will be considered as positive if statistical significance is achieved for primary efficacy endpoints for both baseline platelet count cohorts.

The 95% CI for the proportion of subjects not requiring a platelet transfusion or any rescue procedure for bleeding will be calculated for each treatment group within each baseline platelet count cohort. In addition, the 95% CI for the difference between avatrombopag and matching placebo will also be provided within each baseline platelet count cohort using normal approximation method.

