Since the HCC status is included in the randomization stratification for safety purposes only, not for efficacy consideration, HCC will not be included in the CMH model for the primary efficacy analysis.

Subjects with missing information about the primary efficacy outcome due to early withdrawal or other reasons will be considered as having received a transfusion for the primary analysis.

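### The primary CMH test omits HCC status although randomisation is stratified on it, so the test is conservative and loses a little power if HCC predicts the outcome

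*SAP*

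**What the plan says.** Protocol 9.4.3 stratifies randomisation, within each platelet cohort, by bleeding risk (three levels) and HCC status (two levels). That makes six strata per cohort, with 2:1 allocation "based on a computer-generated randomization scheme using permuted-block randomization". It gives one purpose for both factors: "HCC status (Yes or No), in order to ensure balance between treatments within each cohort and each further stratum". SAP 3.2 repeats the design.

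The primary test in SAP 5.4.1 is a CMH test run separately in each cohort. It adjusts for bleeding risk only, using the Amendment 02 categories. HCC is expressly left out: "HCC will not be included in the CMH model for the primary efficacy analysis". The reason is that "HCC status is included in the randomization stratification for safety purposes only, not for efficacy consideration". SAP 5.3.2, the protocol synopsis (primary efficacy variable analysis) and protocol 9.7.1.6 say the same. The first secondary endpoint uses the same risk-only CMH (SAP 5.4.2.1).

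No sensitivity analysis listed in SAP 5.4.1.1 adds HCC; the Fisher's exact version drops bleeding risk as well. HCC is not among the efficacy subgroups in SAP 5.4.1.2. The only outcome split by HCC is thromboembolic events (SAP 5.6.6.1). HCC status is collected and summarised at baseline (SAP 5.2.4).

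**The concern.** Blocking on a factor forces the arms to be balanced on it. If the factor predicts the outcome, the treatment difference then varies less from trial to trial than it would without blocking. A test that ignores the factor uses the larger, unblocked variance. Its actual size drops below 5% and some power is lost. This depends on how subjects were allocated, so the motive for stratifying (safety or efficacy) makes no difference.

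A cost arises only if HCC predicts transfusion or rescue within a bleeding-risk category. That is possible but not shown. HCC bears on which procedure is done, since ablation or chemoembolization for HCC is a permitted procedure. What is at stake is efficiency and agreement with the design. Both cohorts must succeed for the study to be positive, so any loss per cohort counts twice.

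**Working it through.** **Inputs from the documents.** 100 subjects per cohort, 67 vs 33; placebo response 18%; difference 35 points, so 53% vs 18%; two-sided alpha 0.05; stated power above 90% by Fisher's exact test (SAP 4). Low risk at most 60% and high risk at least 10% of subjects (SAP 3.2).

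**Assumptions, because the documents are silent.** HCC prevalence 25 to 50% in every risk stratum, or concentrated (10/50/50% in low/moderate/high risk); HCC odds ratio 1 to 8; block size 3 or 6; risk mix 60/20/20; null response rates of 18% and, for comparison, 35%.

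**Step 1: the plan's own figure.** Exact enumeration of Fisher's test gives 92.6% power per cohort, which agrees with the stated figure. The normal approximation gives 94.5%.

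**Step 2: size by formula.** Take one risk stratum with HCC prevalence π, response p1 with HCC, p0 without, and overall rate p. The risk-only test uses p(1−p), but balance on HCC removes the between-group part. So

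true variance / assumed variance = R = 1 − π(1−π)(p1−p0)² / [p(1−p)], and actual size ≈ 2[1 − Φ(1.96/√R)].

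With π = 0.25, p = 0.18 and an odds ratio of 8:

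- HCC lowers response: p1 = 0.036, p0 = 0.228. R = 1 − 0.1875 × 0.192²/0.1476 = 0.953; size ≈ 4.5%.
- HCC raises response: p1 = 0.446, p0 = 0.091. R = 1 − 0.1875 × 0.355²/0.1476 = 0.840; size ≈ 3.2%.

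R cannot exceed 1, so on this approximation the error is always conservative. The direction of the HCC effect, which is also unknown, matters to its size.

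**Step 3: simulation.** One cohort of 100, 2:1 permuted blocks within six strata, CMH chi-square without continuity correction. There were 20,000 null runs (standard error about 0.15 points) and 8,000 alternative runs (about 0.25 points) per scenario. HCC is taken to lower response. Each cell gives risk only → risk × HCC, in percent; ranges cover blocks of 3 and 6.

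| HCC prevalence | Odds ratio | Size, 18% null | Size, 35% null | Power |
|---|---|---|---|---|
| 25% throughout | 1 | 4.6 → 4.6 | 4.8 → 4.8 | 94.7 → 94.5 |
| 25% throughout | 2 | 4.6 → 4.8 | 4.6 → 4.8 | 94.2 → 94.4 |
| 25% throughout | 4 | 4.4–4.6 → 4.7–5.0 | 4.2 → 4.8–4.9 | 95.0 → 95.8 |
| 25% throughout | 8 | 4.3–4.4 → 4.7–4.9 | 3.6–4.0 → 4.6–4.9 | 94.7–95.3 → 96.1–96.3 |
| 10/50/50% | 4 | 4.8–4.9 → 5.0–5.1 | 4.6–4.7 → 5.1 | 95.3–95.5 → 95.8 |
| 10/50/50% | 8 | 4.7–4.9 → 5.0–5.1 | 4.3–4.4 → 4.9–5.2 | 95.8–96.0 → 96.6–96.8 |

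The smallest gain at an odds ratio of 4 or more is 95.79 − 95.47 = 0.3 points (10/50/50%, blocks of 6). The largest in the table is 96.14 − 94.73 = 1.4 points (25%, odds ratio 8, blocks of 6). Separate simulations at log odds ratios of 1.4 to 2.0 (odds ratios about 4 to 7.4) gave size of about 3.0 to 4.5% for risk only, about 4.6 to 5.5% with HCC added, and power gains of up to 1.9 points.

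**Step 4: both cohorts.** Treating the cohorts as independent, the 1.4-point case gives 0.9473² = 0.897 → 0.9614² = 0.924, about 2.7 points on the chance of a positive study.

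**The case against.** The exclusion is pre-specified, reasoned and stated identically in protocol and SAP. The risk-only test is valid, errs on the safe side, and keeps about 94 to 96% power in every tabulated scenario. All of that stands.

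The documents do not show that HCC predicts transfusion. They link advanced HCC to portal vein thrombosis (protocol 9.5.1.2), which fits the safety rationale. The HCC-specific procedures sit in the moderate-risk category, which the CMH already adjusts for. A reader might take the procedure table as evidence that HCC is prognostic; it shows overlap with an adjusted factor, and no more. When HCC is concentrated in moderate and high risk, the gain shrinks, as the 10/50/50% rows show.

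Sparse cells are real. With 10% high risk and an assumed 25% HCC, one cell holds 100 × 0.10 × 0.25 = 2.5 subjects on average, and a cell with one arm contributes nothing. With no HCC effect, though, the extra strata changed simulated power by only 0.2 to 0.3 points (94.70 → 94.45).

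Adding HCC may also not reproduce the randomisation exactly. The CMH uses Amendment 02 risk classes, and that amendment revised the classes while the study was running. Subjects randomised earlier may have been stratified differently.

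**Conclusion.** The mismatch is real and its consequence is small. If HCC predicts the outcome within risk category, the planned test runs below its nominal 5%. At an odds ratio of about 4 to 8, size is roughly 3 to 4.6% with HCC spread evenly across risk classes and 4.3 to 4.9% with it concentrated in moderate and high risk. The power forgone is about 0.3 to 1.9 points per cohort. At an odds ratio of 2 or below, the change is about 0.4 points or less, on the order of simulation error. All these figures rest on the assumed prevalence, effect, risk mix and block size.

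Two stronger readings should be set aside. A reader might infer that departing from the randomisation strata inflates false positives or undermines a positive result; the direction is conservative in the formula and in every simulation. A reader might also infer that the study is underpowered; stated power above 90% is met with or without HCC. The case for changing is that the factor is already randomised on and already collected, and the stated reason for omitting it does not bear on the variance.

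**What to change.** Before unblinding:

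- Stratify the CMH for the primary and first secondary endpoints by bleeding risk × HCC status, six strata per cohort, and keep the risk-only CMH as a sensitivity analysis.
- Amend SAP 5.3.2, 5.4.1 and 5.4.2.1, and bring the protocol into line: the synopsis paragraphs on the primary and secondary efficacy analyses, and section 9.7.1.6. Changing the SAP alone would create a contradiction between the documents.
- State which risk classification defines the strata for subjects randomised before Amendment 02.

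If the sponsor prefers not to change the primary test, the minimum is to list the risk × HCC CMH in SAP 5.4.1.1.

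The cost is one more stratification variable in the program and the SAP wording, plus a protocol change if the primary test is replaced. The statistical downside is a few sparse high-risk × HCC cells. No new data are needed.

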## 5.2 STUDY SUBJECTS

### 5.2.1 Definitions of Analysis Sets

Full Analysis Set (FAS): The FAS is the group of all subjects who are randomized into the study.

Per Protocol Analysis Set (PP): The PP is the group of all randomized subjects who receive protocol-assigned study drug and do not meet any of the following criteria:

- Baseline platelet count of  $>50 \times 10^9/L$
- Subjects who were enrolled in the study despite not being planned for transfusion even in the event of no significant increase of platelet count
- Taking prohibited prior medications or prior transfusion
- Presence of significant bleeding at baseline
- Did not have a protocol permitted procedure on Day 8 - 15
- Received dose different from the intended dose
- Received  $<80\%$  of the total dose or received  $>40\%$  of total dose without food
- No elective procedures or elective procedure outside day 8-15
- Subject received platelet transfusion before knowing V4 platelet count
- Subject refused platelet transfusion

Subjects who met any of the criteria listed above will be excluded from the PP due to possible introduction of bias.

Safety Analysis Set: The Safety Analysis Set is the group of subjects who receive at least one dose of study drug and have at least one post dose safety assessment.

The number (percentage) of subjects in each analysis set will be summarized by treatment groups using descriptive statistics. The summaries for FAS and PP will be based on subjects “as randomized”. The summary for Safety Analysis Set will be based on subjects “as treated”.

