### 5.3.2 Adjustments for Covariates

The primary efficacy endpoint, the proportion of subjects without platelet transfusion or any rescue procedure for bleeding, and the first secondary efficacy endpoint, proportion of subjects with platelet count  $\geq 50 \times 10^9/L$  on Procedure Day, will be analysed separately within each

baseline platelet count cohort ( $<40 \times 10^9/L$  or from 40 to  $<50 \times 10^9/L$ ) using the Cochran-Mantel-Haenszel (CMH) test adjusting for the risk of bleeding associated with the elective procedure (low, moderate, or high based on Amendment 02 categorization). Since the HCC status is included in the randomization stratification for safety purposes only, not for efficacy consideration, HCC will not be included in the CMH model for the primary efficacy analysis.

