## 8 DEFINITIONS AND CONVENTIONS FOR DATA HANDLING

### 8.1 VISIT WINDOW

Study Day 1 is defined as the date of the first dose of study drug. The analysis visits defined below will be used in the by-visit summaries:

Visit	Target Visit Date	Visit Window	Analysis Visit
Visit 2 (Baseline)	Study Day 1	Less or equal to Study Day 1	Last visit on or before Study Day 1
Visit 3	Study Day 4	Study Day 2 to 7	Closest visit to Study Day 4
Visit 4	Study Day	Subjects with procedure:	Subjects with platelet

Visit	Target Visit Date	Visit Window	Analysis Visit
(Procedure Day)	10 to 13	Study Day 8 to actual procedure day  Subjects without procedure: Study Day 8 to 13	transfusion: last visit before transfusion  Subjects with procedure but without transfusion: last visit before procedure  Subjects without platelet transfusion or procedure: closest visit to Study Day 10
Visit 5	7 Days post procedure	Subjects with procedure: 1 to 10 days post actual procedure day  Subjects without procedure: Study Day 14 to 20	Subjects with procedure: visit closest to 7 days post actual procedure day  Subjects without procedure: closest visit to Study Day 17
Visit 6	Study Day 35	Subjects with procedure: Greater or equal to actual procedure day +11 days  Subject without procedure: Greater or equal to Study Day 21	Closest visit to Study Day 35

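### Does SAP 5.4.1 need an explicit primary score for subjects who had no elective procedure or who refused a platelet transfusion?

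*SAP*

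**What the plan says.** SAP 5.2.1 defines the Full Analysis Set (FAS) as everyone randomised, and SAP 5.4 makes it the primary efficacy population. SAP 5.4.1 counts as primary responders those "who do not require a platelet transfusion or any rescue procedure for bleeding after randomization and up to 7 days following an elective procedure". Their proportion is tested in each platelet cohort, and both tests must be significant. The only scoring rule in that section is "Subjects with missing information about the primary efficacy outcome due to early withdrawal or other reasons will be considered as having received a transfusion". SAP 8.2 repeats the principle: subjects lacking the needed transfusion data are non-responders.

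The two groups in question appear elsewhere:

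- SAP 8.1 gives subjects without a procedure their own analysis visits, for by-visit summaries: "Subjects without platelet transfusion or procedure: closest visit to Study Day 10" for Visit 4 and "Subjects without procedure: closest visit to Study Day 17" for Visit 5.
- SAP 5.2.1 lists "No elective procedures or elective procedure outside day 8-15" and "Subject refused platelet transfusion" among the grounds for leaving the Per Protocol (PP) set, and explains: "Subjects who met any of the criteria listed above will be excluded from the PP due to possible introduction of bias".

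SAP 5.3.2, on covariate adjustment, describes the endpoint as "the proportion of subjects without platelet transfusion or any rescue procedure for bleeding". Protocol 9.5.1.3 has the case report form carry a Not Done or Not Applicable entry for a subject who was not transfused. SAP 5.4.1.1 lists four sensitivity analyses: PP, observed case, Fisher's exact test, and an endpoint without the rescue component. SAP 9 places derivation rules in separate documents, which are not available here.

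**The concern.** The sponsor expected both groups and regarded them as a source of bias, yet the SAP does not score either by name in the confirmatory analysis.

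A subject with no procedure may have a complete record showing no transfusion. One analyst could score a responder. Another could say that the follow-up window never opened, so the outcome is missing and counts as transfused. A refuser was not transfused, which fits the phrase in SAP 5.3.2, but did need a transfusion, which fails the definition in SAP 5.4.1.

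None of the four sensitivity analyses rescores these subjects within the FAS. PP removes them, observed case touches only missing outcomes, and the other two inherit whatever score was chosen. Because one failed cohort makes the study not positive, a coding choice made after unblinding could matter if the groups were large or unequal between arms.

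**Working it through.** **Step 1. Read the rules together.**

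*Refused transfusion.* The endpoint definition (SAP 5.1.1), the variable, hypotheses, test and confidence interval (SAP 5.4.1), the modified endpoint (SAP 5.4.1.1) and Protocol 9.7.1.1 and 9.7.1.6 all speak of not requiring a transfusion. SAP 5.3.2 is a shorthand in a section about covariates. On the governing wording, a subject who needed a transfusion and refused it is a non-responder.

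*No procedure.* The endpoint needs status to 7 days after the procedure. With no procedure, that status cannot exist. The missing-outcome rule in SAP 5.4.1 extends beyond early withdrawal to other causes, and SAP 8.2 covers anyone without the required transfusion data. The natural result is non-responder. For a procedure done outside the study (Protocol 9.3.3), continued follow-up, the concomitant-therapy records (Protocol 9.4.7) and the resource-use records (Protocol 9.5.1.6) can capture a transfusion. Where they do not, the missing rule applies.

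**Step 2. Reproduce the planned power.** Inputs from SAP 4: 67 versus 33 per cohort, 18% on placebo, a difference of 35 points (so 53%), Fisher's exact test, two-sided 0.05, power above 90%.

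Power = Σx Σy Bin(x; 67, pA) · Bin(y; 33, pP), summed over outcomes with Fisher p ≤ 0.05. At 53% and 18% this is 92.6% per cohort, and 0.926² = 85.8% for both if independent. The stated figure holds.

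**Step 3. Effect of the coding for no-procedure subjects.** Let q be their share of an arm, unrelated to response. The documents give no q, so the values below are assumptions.

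- Scored responder: p(1 − q) + q
- Scored non-responder: p(1 − q)

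The two treatment differences are therefore qA − qP apart, which is zero when the shares are equal.

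| Share, avatrombopag / placebo | Difference: responder / non-responder (points) | Power: responder / non-responder |
|---|---|---|
| 2% / 2% | 34.3 / 34.3 | 90.7% / 91.9% |
| 3% / 0% | 36.4 / 33.4 | 94.3% / 90.4% |
| 10% / 0% | 39.7 / 29.7 | 97.1% / 83.3% |
| 0% / 10% | 26.8 / 36.8 | 68.3% / 95.4% |

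Example for 3%/0%: 0.53 × 0.97 + 0.03 = 0.544 and 0.53 × 0.97 = 0.514, each less 0.18.

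**Step 4. Effect of the coding for refusers.** Let f be the fraction who refuse among those needing transfusion. Non-responder coding leaves p unchanged: 35 points and 92.6%. Responder coding gives p + (1 − p)f. With equal f in both arms, the difference changes by f(0.47 − 0.82) = −0.35f. At f = 2%, 5% and 10% it is 34.3, 33.25 and 31.5 points, with power 90.7%, 87.7% and 82.2%. Responder coding with equal refusal thus works against avatrombopag.

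**Step 5. False positives favouring avatrombopag, true rate 18% in both arms.** With no such subjects, the rate per cohort is 1.65%.

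| Share, avatrombopag / placebo | Responder coding | Non-responder coding |
|---|---|---|
| 3% / 0% | 3.2% | 1.4% |
| 10% / 0% | 11.3% | 0.9% |
| 0% / 10% | 0.1% | 2.7% |

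At 10%/0% with responder coding and no effect in either cohort, the both-cohort rule gives 0.113² = 1.3%. If one cohort has no effect and the other has the full 35 points, with the same split in both, it gives 0.113 × 0.971, or 10.9% from unrounded values.

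**Step 6. How many subjects would have to move.** At close to the planned rates, 36/67 versus 6/33 gives p = 0.0011. Four more placebo responders leave p = 0.034, and five give p = 0.060. Moving 10 avatrombopag responders to non-responder leaves p = 0.043, and 11 gives p = 0.067. Losing a cohort therefore needs 5/33 = 15% of placebo or 11/67 = 16% of avatrombopag subjects recoded in one direction.

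**The case for a change.** The strongest case for a change is that the SAP foresaw both groups, called them a possible source of bias, and then left their primary score to inference. Unequal shares are conceivable. Investigators may delay a procedure when the platelet count exceeds 200 × 10⁹/L (Protocol 9.1.2.3), which would be expected mainly on active drug. Protocol 7.1 says that refractoriness to transfusion can lead to delayed or cancelled procedures. PP deletes subjects on post-randomisation events, so it does not show the randomised comparison under the other score. A sentence and a table would be cheap.

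Part of this stands. No passage explicitly assigns a fully recorded no-procedure subject, or says how need is derived from a form that records receipt. The argument that the window never opened does not reach refusers, who depend on the endpoint wording alone.

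The case for material harm is weaker. The platelet mechanism permits delay, and Protocol 7.2 and 9.4.4 aim to keep counts above 200 × 10⁹/L below 2% of subjects. No passage supports a 10% one-sided share. The added sentence would mostly write down what SAP 5.4.1 and 8.2 already imply. Its coding is not uniformly conservative either: with 10% of placebo subjects and no avatrombopag subjects lacking a procedure, false positives rise from 1.65% to 2.7% per cohort. A refusal rule tied to the investigator's view of need may also require data that the documents do not show being collected. PP already gives one prespecified look without these subjects, and SAP 5.4.1.1 allows further sensitivity analyses.

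**Conclusion.** The SAP is silent on these two groups by name, but it states no rule that gives a wrong answer. The formal endpoint wording makes refusers of a needed transfusion non-responders. The missing-outcome rule most naturally does the same for subjects whose post-procedure window never opened. Analysts can apply both readings without amending the plan, and the separate derivation documents are the usual place for this detail.

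For no-procedure shares of 2%/2% or 3%/0%, power per cohort stays above 90% under either score, and the treatment difference moves by at most 3 points. Refusal by 2% of those needing transfusion also leaves power above 90% if refusers are scored as responders. The choice becomes important only with much larger shares, such as the one-sided 10% splits for which the documents give no basis.

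These figures assume the planning rates of 53% and 18%, no-procedure status unrelated to response, and Fisher's exact test as in the sample-size section. The primary test is the Cochran-Mantel-Haenszel test stratified by bleeding risk, so they are close guides and not exact operating characteristics. They would need another look if either group proved to be common or clearly unequal between arms.
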